1.4 Gabapentin

Gabapentin is a drug structurally similar to GABA that interacts with voltage calcium channels located throughout cortical brain tissue[32, 33]. Although labeled for treatment of partial seizures, Gabapentin's unlabeled indications include treatment of neuropathic pain conditions such as restless leg syndrome, diabetic neuropathy, fibromyalgia and migraines [33-35]. The question has been raised as to whether Gabapentin can decrease radiation-induced acute and chronic oral mucositis pain in head and neck cancer patients. The majority of data looking at Gabapentin in management of acute and chronic pain has taken been done in the setting of post-operative management. A review of Gabapentin in the treatment of acute post-operative pain by Chang et al found that the administration of gabapentin was associated with post-operative reductions of (1) rescue analgesics and pain scores in patients undergoing coronary artery bypass graft, (2) the requirements of antiemetics in patients undergoing neurological surgery and hysterectomy, and (3) a reduction in pain and narcotic use in patients undergoing lumbar spinal surgery at every time point [36]. A second study by Straube et al found that single 250 mg dose of Gabapentin was associated with 50% reduction in acute pain over 6 hours post-operatively (RB of 2.5 with 95% CI 1.2 to 5.0) in 15% of patients vs only 5% in controls as well as a decreased usage of rescue medications [37]

A study looking at the effects of Pregabalin, a drug structurally similar to Gabapentin, found that Pregabalin is effective at reducing neuropathic and inflammatory orofacial pain in rat models [38]. Gabapentin has also been found to improve dysphagia in patients with oropharyngeal squamous cell carcinoma (OPSCC). A case report of 10 head and neck cancer patients treated with gabapentin after failing other interventions found that three 300 mg doses of gabapentin daily eliminated neuropathic pain in 8 of the 10 patients with partial relief of symptoms in the remaining 2 [39]. A study by Starmer et al found that prophylactic treatment of Gabapentin in patients with OPSCC was associated with delayed onset of PEG use (3.7 vs 2.29 week; P=0.013) and earlier removal of their PEG tubes (7.29 vs 32.56 weeks; P=0.039) than controls [40]. Thus it is plausible that treatment of oral mucositis with Gabapentin can be

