hypothesized to improve not only pain but also improve quality of life parameters such as swallowing and nutritional intake.

A retrospective study evaluated this question. Investigators conducted a chart review of 42 patients with head and neck malignancies treated with concurrent chemoradiotherapy using an intensity-modulated radiotherapy technique. Pain outcomes for patients treated with gabapentin for prevention of mucositis associated pain were compared to pain outcomes for patients using standard supportive care. Results found that preventive administration of gabapentin reduced overall pain levels and the total dose of opioids utilized [34]. Although the data is intriguing, there are numerous limitations to this study. First, the study was retrospective. Second, patients were not randomized and third, outcomes were not pre-established. None-the-less, the data would support further investigation of gabapentin as chronic preventive measures for mucositis associated pain in patients undergoing chemoradiation for head and neck cancer

1.6 Study Summary:

The overall goal of this study is to determine whether or not Gabapentin can reduce mucositis associated pain in head and neck cancer patients undergoing chemoradiation. Patients seen in the Oncology Clinic for routine surveillance will be informed about the study and asked if they interested in participation. Interested patients will be asked to sign an informed consent. They will then be randomized into to two arms—standard of care and standard of care plus gabapentin. Prior to chemoradiation therapy, subjects will undergo education on chemoradiation as well as foundations of oral care. Subjects will be asked to complete a demographic survey, the Head and Neck Symptom Survey 2.0 plus the General Symptom Survey (VHNSS v2.0 plus GSS), the Profile of Mood States – short form (POMS-SF), the Neurotoxicity Rating Scale (NRS), the and a Quality of Life (QOL) assessment as outlined below. Subjects will also be requested to maintain a pain diary that will be used throughout the study to assess their pain and their mucositis will be graded weekly during their visits.

Upon completion of therapy, the data will be collected and stored in a secure password protected database and the patient's study participation will end. We anticipate the study duration to be 2 years.

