2.0 Specific Aims

Specific Aim 1: To determine whether Gabapentin used as a preventive measure during chemoradiation can reduce radiation-induced mucositis associated pain in head and neck cancer patients as measured by: 1) pain scores on the Vanderbilt Head and Neck Symptom Survey (VHNSS version 2.), and 2) analgesic use.

Hypothesis 1.1: Compared to controls, patients using Gabapentin during radiation-based therapy will have a 1.5 point decreases in self-reported oropharyngeal pain (on a scale of 0 to 10) week six of radiation.

Hypothesis 1.2: Compared to controls, patients using Gabapentin during radiation-based therapy will have a 20% decrease in opioid use (as measured in morphine equivalents) at week six of radiation.

Specific Aim 2: To determine whether pain control is associated with weight loss (in pounds) and duration of use of percutaneous endoscopic gastrostomy utilization (in days).

Hypothesis 2.1 Patients with less pain will have decrease weight loss.

Hypothesis 2.2 Patients with less pain will have a shorter duration of PEG placement.

Specific Aim 3: To assess the safety (grade 3 or 4 adverse events) and tolerability of using gabapentin (discontinuation of drug due to side effects - yes or no).

Specific Aim 4: To correlate pain severity with frequency and severity of general systemic symptoms.

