Study Visit: The study nurse will meet with the patient at baseline, weekly during radiation therapy, and at 1, 2 and 3 months post-treatment. At each study visit the study nurse will 1) administer appropriate questionnaires, 2) review the patient's pain diary and compliance diary, 3) document concurrent medications, 4) document toxicities based on CT CAE criteria 4.0, 5) identify and prepare reports for any adverse events, 6) document any dose adjustments in pain medications as recommended by the physician or nurse practitioner, and 7) educate the patient regarding medication dose and schedule.

As these patient reported outcome measures represent outcomes of interest for the study, they will not be altered by study staff due to missingness as changes would threaten the validity of the tool.

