Appendix I: Studies to be Done:

	Baseline¥	Week 1	Week 2	Week 3	Week 4	Week 5	Week 6 *	Week 7 *	1,2 3 Months post tx
Study Visit	X	X	X	X	X	X	X	X	X
Chemoradiation Teaching	X								
Foundations of Oral Care	X								
Foundations of Pain Management	X								
Randomization	X								
Gabapentin Arm 2 Only		X	X	X	X	X	X	X	X
Mucositis Grading	X	X	X	X	X	X	X	X	X
Demographic Survey	X								
VHNS Version 2.0		X	X	X	X	X	X	X	X
Pain Survey		X	X	X	X	X	X	X	X
Compliance Survey Arm 2 Only		X	X	X	X	X	X	X	X
Neurotoxicity Scale	X						X		X (month 3 only)
POMS	X						X		X (month 3 only)
QOL	X						X		X (month 3 only)

Disease and Treatment Form	X								
----------------------------	---	--	--	--	--	--	--	--	--

‡ All baseline assessments must be done within 4 weeks before starting concurrent chemoradiation.

* Weekly assessments will continue until the completion of chemoradiation which may vary between 5 and 7 weeks.

An End of Treatment Visit will be conducted 2 weeks after Chemoradiation therapy

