Analyses for study aims. Graphical and descriptive statistical summaries will be generated for all study variables. Evaluation of the key outcome variable data distributions (VHNSS mouth pain scores, opioid dose) will inform the required test distribution (e.g., normal, log-normal). Mixed-level general linear modeling will be used to test study hypotheses. Given that patients will have varying VHNSS pain scores prior to beginning radiation, those baseline values will be included as a covariate in the analyses of outcomes [EOT: VHNSS pain scores (H1.1); opioid use (H1.2); weight loss (H2.1); duration of PEG (H2.2); general symptoms (Aim 4)]. Frequency distributions will summarize the safety and tolerability outcomes (Aim 3). All tests of statistical significance will maintain maximum Type I error of 0.05 ($p < 0.05$).

Sample size justification. The proposed sample size was based on typical VHNSS pain score values during/end-of-treatment in prior studies (M=4.5, SD=2.8). A total sample size of 120 patients (60 per arm) who complete the protocol will provide 80% statistical power (2-tailed alpha=0.05) to detect a decrease of 1.5 points on the VHNSS pain scale due to the addition of gabapentin to usual care. Given a change of 2.0 points on the scale is proposed to be clinically meaningful, this slightly larger sample size will provide coverage in the case that our sample values are slightly more variable than those observed in our prior studies. A total sample size of 120 will also enable us to detect correlations as small 0.25(6.3% shared variance) with 80% power and 2-tailed alpha=0.05. We expect clinically meaningful associations to be larger than this value.

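### H2.2 puts PEG duration in days into a linear model, but scheduled contact may end while tubes are still in place, and no rule covers those tubes or patients who never have one

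*Combined protocol and SAP*

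**What the plan says.** Specific Aim 2 (section 2.0) names the outcome as "duration of use of percutaneous endoscopic gastrostomy utilization (in days". Hypothesis 2.2 reads "Patients with less pain will have a shorter duration of PEG placement". The first speaks of use, the second of placement.

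Section 10.0, under the analyses for study aims, says "Mixed-level general linear modeling will be used to test study hypotheses". Its list of outcomes adjusted for baseline VHNSS pain runs "EOT: VHNSS pain scores (H1.1); opioid use (H1.2); weight loss (H2.1); duration of PEG (H2.2", so PEG duration stands in a bracket opened by EOT. The check of data distributions in that paragraph names only mouth pain scores and opioid dose.

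On the length of observation, section 6.2 schedules visits "weekly during radiation therapy, and at 1, 2 and 3 months post-treatment", and both copies of the Appendix I calendar agree. The calendar footnote says "Weekly assessments will continue until the completion of chemoradiation which may vary between 5 and 7 weeks". Section 1.6, however, says that once therapy is completed and the data are collected, "the patient's study participation will end".

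Section 1.4 cites an earlier study of prophylactic gabapentin that found "earlier removal of their PEG tubes (7.29 vs 32.56 weeks; P=0.039) than controls". It gives neither the time origin nor the distribution of those figures.

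**The concern.** A tube still in place at last contact has a duration known only to exceed the time observed. A general linear model has no place for such a value: the analyst either enters last contact as if it were removal, or leaves the patient out. The missing-data text in section 10.0 expects two kinds of gap, skipped items and assessments lost to follow-up. A patient who attends month 3 with the tube in place is neither. Nor does the text say whether a patient who never has a PEG counts as zero days or is excluded.

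The start (placement or first use) and the cut-off (month 3 or end of treatment) are open as well. Several different slopes could come from the same data, all compliant with the plan, and a rule chosen after the data are seen could be driven by the result. If unresolved tubes are numerous, the estimated association between pain and PEG duration is pulled toward zero.

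**Working it through.** **1. The plan's nearest figure.** No power is stated for PEG duration. Section 10.0 claims 80% power for a correlation of 0.25 with 120 patients, two-sided alpha 0.05. By Fisher's z, power = Φ(atanh(0.25) × √(120−3) − 1.96) = Φ(0.2554 × 10.817 − 1.96) = Φ(0.80) = 0.789. This agrees with the stated figure and assumes 120 complete pairs.

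**2. Observation window.** Treatment lasts 5-7 weeks and month 3 is about 13 weeks later: 5+13 = 18 and 7+13 = 20 weeks from the start of radiation. A tube placed at the end of treatment is followed for about 13 weeks, and one placed on the first day of a 7-week course for about 20. Hence a range of 13-20 weeks. A cut-off at end of treatment would be shorter still.

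**3. Share of tubes still in place.** Assume exponential durations from placement, with the section 1.4 figures as means; share = exp(−window/mean).
- Mean 32.56 weeks: exp(−13/32.56) = 0.671; exp(−20/32.56) = 0.541.
- Mean 7.29 weeks: exp(−13/7.29) = 0.168; exp(−20/7.29) = 0.064.

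Other assumptions for 32.56 weeks give 43-54% (Weibull, shape 0.7), 74-88% (Weibull, shape 2) and 65-76% (exponential, 32.56 as a median). If 32.56 weeks is a mean duration, a similar population must contain durations beyond 20 weeks, whatever the distribution.

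**4. Effect on the linear analysis.** Large-sample simulation with a Gaussian copula, latent correlation 0.25 and pain SD 2.8 (section 10.0), at mean 32.56 weeks:

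| Handling | Correlation | Days per pain point |
|---|---|---|
| All durations known | 0.23 | 18.4 |
| Capped at 13 / 20 weeks | 0.20 / 0.22 | 1.9 / 3.6 |
| Unresolved tubes dropped, 13 / 20 weeks | 0.12 / 0.14 | 1.2 / 2.0 |

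The slope equals correlation × SD of days ÷ SD of pain. In full: 0.226 × 227.9/2.8 = 18.4. Capping at 13-20 weeks cuts the SD of days from 228 to 27-47, so 0.199 × 27/2.8 = 1.9 and 0.215 × 47/2.8 = 3.6. Most of the fall under capping is thus a narrower outcome scale, not a weaker association.

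At mean 7.29 weeks the slope is 4.1 in full, 2.6-3.4 capped and 1.6-2.5 dropped; capping does not lower the correlation (0.225 in full, 0.234-0.236 capped).

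**5. Dependence on the model.** With a log-linear effect of 0.25 per SD of pain on an exponential mean of 32.56 weeks and n = 120, capping costs more: power falls from about 75% to 39% at 20 weeks and 28% at 13 weeks. At 7.29 weeks it falls from 75% to 72% and from 74% to 64%.

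**6. If only PEG users are analysed.** The documents give no placement rate. If an assumed 30-70% of 120 have a PEG (36-84 patients), power for r = 0.25 is Φ(0.2554 × √33 − 1.96) = 0.31 to Φ(0.2554 × √81 − 1.96) = 0.63.

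**The case against.** Censoring is possible but not shown. Section 5.1 provides for chart review after therapy without an end date. It speaks of disease treatment data, but if removal dates were abstracted late enough, much of the censoring would go. Tube status is also collected: the VHNSS opens with a yes/no item on whether a feeding tube is in place, and the calendar schedules it weekly and at months 1, 2 and 3. This stands in part. The item brackets removal within a week or a month; it does not give days, and it says nothing after month 3. Appendix H shows no PEG date field.

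A reader might infer from the slope falling from about 18 to 2-4 days that capping destroys the test of H2.2. The documents do not support that. H2.2 is directional, section 10.0 frames power in correlations, and under the copula model capping barely lowers the correlation. The larger loss in step 5 rests on a different assumed model. Dropping unresolved tubes is the more harmful rule in the copula illustration, but the plan does not say that it would be used.

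The inputs are also assumptions: the time origin and distribution of the cited removal times are not given, and 0.25 is the plan's detectable correlation, not an expected one.

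None of this supplies the missing rules, which are absent whatever the simulation shows.

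**Conclusion.** The point holds as a gap in method and definition for a secondary hypothesis. The plan assigns a duration in days to a linear model, schedules contact for at most about 20 weeks from the start of radiation, and cites a control removal time of 32.56 weeks. It has no rule for start, cut-off, unresolved tubes or non-users.

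The size depends on the unknown duration distribution and on the rule used: potentially a halving of the correlation if unresolved tubes are dropped and removal resembles the cited control figure, and much less at the gabapentin figure. These are illustrations, not predictions. It does not follow that censoring is certain, or that the primary pain comparison or its sample size is affected; neither uses PEG duration.

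**What to change.** A cheap improvement, to be fixed before data review. Choose one:

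- **(a) Time to removal.** Among PEG recipients, analyse time from one stated start to removal, reconciling use in Aim 2 with placement in H2.2. Censor at last contact, treat death as a competing event, and enter VHNSS pain as a time-varying covariate so that tubes removed before end of treatment are kept. PEG receipt may itself depend on pain, so also report receipt (yes/no) against pain in all patients.
- **(b) Bounded outcome.** Redefine the outcome as PEG days through month 3, score non-users 0, label it as bounded, use a two-part or ordinal model, and state a rule for death or dropout before month 3.

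Under either option:
- Reconcile section 1.6, section 6.2 and the EOT label in section 10.0 on when observation ends.
- Record PEG start and removal dates from chart review, with the VHNSS feeding-tube item as an interval-level source.
- Keep the baseline pain covariate only if VHNSS is added at baseline, since neither copy of the calendar marks it there.

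The cost is wording and a little chart abstraction; no extra patients are needed. Option (a) yields a hazard ratio instead of days and, if hazards are not proportional, one that depends on the window (0.92 uncensored against 0.88-0.89 at 13-20 weeks in the copula data). It also uses fewer patients, so the 80% power sentence would not carry over to it.

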Prior to initiating therapy, patients will undergo education sessions with study staff. The educational intervention will include a discussion of oral health foundations as well as a discussion of pain management. This education is standardly applied to all VUMC patients undergoing radiation therapy for HNC and will not be otherwise documented. In addition, patients will also be given written material to review. Patient will be given a pain diary and instructed on its use. Baseline pain medication use will be documented. Patients will complete the demographic survey. Patients randomized to gabapentin will be given a prescription for gabapentin with dose escalation as noted in the treatment section. Patients who do not have insurance or who are unable to afford gabapentin will be provided with medication from the indigent pharmacy. All baseline assessments must be done within 4 weeks of starting concurrent chemoradiation.

Weekly On Treatment Visits:

Starting with the initiation of concurrent chemoradiation, patients will be evaluated on a weekly basis. The evaluation will include:

- 1) review of the weekly pain survey
- 2) for patients on gabapentin (Arm 2) --we will review their compliance log and identify any barriers to compliance and strategies to improve their compliance
- 3) adjustment of pain regimen
- 4) completion and review of the Vanderbilt head and neck symptom survey
- 5) mucositis grading.

End-of-Treatment Visit:

Patients will undergo an evaluation at their final radiotherapy visit or within 2 weeks after. This will include the following:

- 1) review of the monthly diary survey
- 2) for patients on gabapentin (Arm 2) --we will review their compliance log and identify any barriers to compliance and strategies to improve their compliance

- 3) adjustment of pain regimen
- 4) completion and review of the Vanderbilt head and neck symptom survey
- 5) mucositis grading.

6.0 Study Measures:

6.1 Mucositis Grading:

Patients will have an oral exam twice a week as part of standard of care. Mucositis will be graded based on the World Health Organization criteria. Mucositis assessments will be done by trained study staff.

6.2 Patient Reported Outcome Measures:

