Appendix I: Study Procedure Calendar

	Baseline‡	Week 1	Week 2	Week 3	Week 4	Week 5	Week 6 *	Week 7 *	1,2 3 Months post tx
Study Visit	X	X	X	X	X	X	X	X	X
Chemoradiation Teaching	X								
Foundations of Oral Care	X								
Foundations of Pain Management	X								
Randomization	X								
Gabapentin Arm 2 Only		X	X	X	X	X	X	X	X
Mucositis Grading		X	X	X	X	X	X	X	X
Demographic Survey	X								
VHNSS Version 2.0		X	X	X	X	X	X	X	X
Pain Survey		X	X	X	X	X	X	X	X
Compliance Survey Arm 2 Only		X	X	X	X	X	X	X	X
Neurotoxicity Scale	X						X		X (month 3 only)
POMS	X						X		X (month 3 only)
QOL	X						X		X (month 3 only)
Disease and Treatment Form	X								

‡ All baseline assessments must be done within 4 weeks before starting concurrent chemoradiation.

* Weekly assessments will continue until the completion of chemoradiation which may vary between 5 and 7 weeks.

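### Section 10 adjusts five analyses for pre-radiation VHNSS pain, but neither study calendar schedules the VHNSS at baseline and no rule covers a patient without a baseline score

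*Combined protocol and SAP*

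**What the plan says.** **Analysis.** Section 10.0, in the paragraph on analyses for study aims, says: "Given that patients will have varying VHNSS pain scores prior to beginning radiation, those baseline values will be included as a covariate". The outcomes listed are VHNSS pain (H1.1), opioid use (H1.2), weight loss (H2.1), PEG duration (H2.2) and general symptoms (Aim 4).

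**Schedule.** Appendix I appears twice. In the table after the instrument descriptions the row is labelled "VHNS Version 2.0"; in the one at the end of the document it is "VHNSS Version 2.0". Both rows are blank at Baseline and marked for Weeks 1 to 7 and the post-treatment months. Both tables carry the footnote "All baseline assessments must be done within 4 weeks before starting concurrent chemoradiation", so a Week 1 form is not a baseline form by the plan's own definition.

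**Visit text.** Section 5.6 lists "completion and review of the Vanderbilt head and neck symptom survey" at the weekly visits and again at the end-of-treatment visit, but not under Baseline. On the weekly visits it says: "Starting with the initiation of concurrent chemoradiation, patients will be evaluated on a weekly basis".

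**Study summary.** Section 1.6, just after a sentence on education before treatment, says: "Subjects will be asked to complete a demographic survey, the Head and Neck Symptom Survey 2.0 plus the General Symptom Survey". The list ends with "a Quality of Life (QOL) assessment as outlined below", which leaves the timing to later sections. Section 6.2 includes a baseline visit but does not name the questionnaires given there.

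**Missing data.** Section 10.0 foresees missing items within an instrument and assessments lost to follow-up, and cites a published strategy for missing outcomes. It applies intent-to-treat to every analysis.

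**The concern.** The analysis section depends on a measurement that the schedule does not collect. Site staff and whoever builds the online forms work from the calendar. If they follow it, the adjusted models for all five analyses cannot be fitted as written. The analyst would then have to choose, after the data are in, between three options: drop the covariate, use a later score in its place, or exclude patients.

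The Week 1 score is the obvious substitute, but it is taken after randomisation and in the column where gabapentin starts. Adjusting for it could absorb part of any early effect on pain or opioid use (H1.1, H1.2). H2.1, H2.2 and Aim 4 are stated as associations with pain, so for them the problem is only that the named covariate is absent.

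A second gap would remain even with a baseline form on the calendar. Some patients will not complete it, and a regression model drops a patient with a missing covariate by default. That conflicts with the intent-to-treat commitment.

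**Working it through.** **1. Is the blank cell real?** In both calendars the Study Visit row has nine marks and the VHNSS row eight; the absent one is Baseline. In the same tables the Neurotoxicity Scale, POMS and QOL rows keep their Baseline mark, so a fault in text extraction is unlikely. The Pain Survey row is also blank at Baseline, so the calendars schedule no pre-treatment pain score of any kind.

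**2. Does another section fill the gap?** The Baseline text of Section 5.6 covers education, handing out the pain diary, recording pain medication and the demographic survey. Its silence alone proves little, because POMS, NRS and QOL are not named there either; but the calendars mark those three at Baseline and do not mark the VHNSS. Sections 1.6 and 6.2 show intent without scheduling the form.

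**3. Does a missing-data rule apply?** Proration needs at least 75% of an instrument's items, so it can rescue a partly completed baseline form but not an absent one. The cited strategy is invoked for outcomes.

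**4. Size for H1.1.** Inputs from Section 10.0: 60 completers per arm, SD 2.8, difference 1.5 points, two-sided alpha 0.05. The documents give neither the correlation r between baseline and outcome nor the share m of missing baselines, so both are assumed. Baselines are taken as missing at random. Power is from the noncentral t distribution.

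*The plan's own figure.* SE = 2.8 × √(2/60) = 0.511. Noncentrality = 1.5/0.511 = 2.93, df 118. Power is 82.9% and the 95% CI half-width 1.01. The stated 80% is met with a small margin; by t-test, 80% needs 56 per arm. Section 10.0 describes its sample size as slightly larger to cover extra variability, so this is not an error.

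*Baseline available for all 120.* Residual SD = 2.8 × √(1 − r²), df 117.

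| r | Residual SD | Power | Half-width |
|---|---|---|---|
| 0.1 | 2.79 | 83.3% | 1.01 |
| 0.2 | 2.74 | 84.4% | 0.99 |
| 0.3 | 2.67 | 86.2% | 0.97 |
| 0.5 | 2.42 | 91.9% | 0.88 |

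*Some baselines missing.* If those patients are dropped, n = 60(1 − m) per arm with the same residual SD and df 2n − 3. If they are kept with the baseline mean pooled over both arms, residual SD = 2.8 × √(1 − r²(1 − m)) with all 120 and df 117.

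| m | Handling | r = 0.3 | r = 0.5 |
|---|---|---|---|
| 10% | dropped (54 per arm) | 82.4% | 89.0% |
| 20% | dropped (48 per arm) | 77.7% | 85.1% |
| 20% | kept, pooled mean | 85.6% | 90.2% |

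A simulation of 6,000 runs at m = 20% agrees: 77.2% and 84.6% dropped, 84.9% and 89.8% with the pooled mean, 84.6% and 89.6% with a missing-indicator. The mean estimated effect was 1.49 to 1.50 throughout.

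*Break-even.* Dropping patients gives less power than no adjustment (82.9%) once n falls below 54.7 per arm at r = 0.3, that is 120 − 2 × 54.7 = 10.6, about 11 patients. At r = 0.5 the limit is 45.3 per arm, or about 30 patients.

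*Every baseline missing.* This is what the calendar as written produces. No imputation rule helps, and the analysis reduces to the unadjusted 82.9%.

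No SDs are given for H1.2, H2.1, H2.2 or Aim 4, so the loss there is not quantified.

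**The case against.** The strongest reply is that this is clerical. Every other instrument in the Section 1.6 list is marked at Baseline in the calendars, and the calendars are loose elsewhere: they disagree with each other on baseline mucositis grading. That stands as an account of how the gap arose. It does not close it, because both calendars omit the VHNSS at Baseline and no other section schedules it.

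A second reply is that a Week 1 score may serve. The VHNSS asks about the past week and weekly visits begin with chemoradiation, so a form completed on the first day would describe the week before radiation. That is possible, but the documents do not fix the day. Section 1.2 puts pain onset two to three weeks into treatment, so any early effect absorbed is likely small; its size is unknown.

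A third reply is that little is lost. With pain starting that late, pre-radiation pain may predict week-six pain weakly, and at r = 0.1 to 0.2 adjustment adds about 0.4 to 1.5 percentage points of power. Monthly database checks (Section 11.0) could also reveal the absent form early. Both points limit the size of the loss. They do not make the planned model fittable for patients already treated.

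Finally, the scenarios with 10% or 20% missing concern a corrected calendar, not the present one. That is correct, and it makes the missing-baseline rule the secondary part of this point.

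**Conclusion.** The inconsistency holds. Section 10.0 needs a pre-radiation VHNSS pain score for five analyses, and the operating schedule does not collect one. The randomised comparison and the stated 80% power survive without it. For H1.1 the cost is precision: at most about 9 percentage points of power (91.9% against 82.9%) and 0.13 points of half-width at r = 0.5, and close to nothing at r = 0.1.

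The reason to correct it is that a pre-treatment score cannot be obtained afterwards, and that its absence would force an unplanned choice of model. The absence of a rule for missing baselines matters less, but dropping patients would conflict with intent-to-treat and could cost more precision than the covariate gains. The figures rest on the plan's SD of 2.8 and on assumed values of r and m. The contradiction between the sections rests on no assumption.

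**What to change.** - Mark the VHNSS 2.0 in the Baseline column of both Appendix I calendars, list it under Baseline in Section 5.6, and assign the online form to the baseline visit.
- Require completion before the first gabapentin dose and the first radiation fraction, and state that a later score is not used as the baseline covariate.
- Add to the missing-data plan that patients without a baseline score stay in the intention-to-treat models for H1.1 and H1.2, for example with the baseline mean pooled over both arms or a missing-indicator.
- Name a separate method, such as multiple imputation, for H2.1, H2.2 and Aim 4. The two devices above suit randomised comparisons, not associations.
- Optional: add the Pain Survey at baseline, and have the baseline forms completed before the arm is revealed.

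The cost is an edit to two tables and one visit list, a short addition to the missing-data plan, and one questionnaire of under 10 minutes (the time given in the plan's VHNSS description) at a visit that already takes place.
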